8.5.3. Pharmacokinetic Statistical Methodology

8.5.3.1. Dose Proportionality Assessment (Parts A and B)

A statistical analysis will be conducted to investigate the dose proportionality of $AUC_{0-t_{last}}$, $AUC_{0-\infty}$, and C_{max} on profile day 1 in Part A, and $AUC_{0-t_{last}}$, AUC_{0-t} , and C_{max} on profile day 14 in Part B (only for plasma CCI)

The analysis is planned to be conducted across full dose range, however if at the time of analysis there isn't sufficient data in some of the dose levels or the dose proportionality is not concluded for the full dose range, analysis across narrower dose range may be explored.

The PK parameters will be analysed using a power model⁴ that will have the following form:

$$parameter = intercept \times dose^{slope} \times random\ error$$

Using the natural log (ln) transformation,⁵ a power model can be expressed as a linear regression equation:

$$\ln(parameter) = intercept + slope \times \ln(dose) + random\ error$$

For dose proportionality, the slope of the regression line is equal to 1; for dose independence, it is equal to 0.

For each PK parameter separately, a pooled estimate (across all doses) of slope, corresponding 95% confidence interval (CI), and between-subject CV will be calculated. Figures (on the logarithmic-logarithmic scale) containing individual values, the power model line (95% CI), and the dose proportionality line (defined as the power model line with slope of 1) will be created for each PK parameter. Additionally, figures (on the logarithmic-linear scale) containing individual values and geometric means will be created for each corresponding PK parameter normalised by dose administered.

The lack of fit test will be conducted for the statistical assessment of linearity assumption, and thus appropriateness of a power model. The lack of fit model will be the same as the power model fitted, but with dose included as an additional fixed effect. The statistical assessment will rule the linearity assumption acceptable if the diagnostic plots appear reasonable and the lack of fit 2-sided p-value >0.05 (dose effect is not significant at the 0.05 level of significance). The assessment of linearity assumption may also occur via visual examination of the figures by the pharmacokineticist. This assessment may override the statistical assessment, where this occurs, it will be detailed in the CSR.

If the assumption of linearity is ruled acceptable and the 95% CI for the slope spans 1, it will be deemed that there is no statistical basis to conclude a lack of proportionality.

If the assumption of linearity is ruled unacceptable for any PK parameter, its corresponding PK parameter normalised by dose administered will be ln-transformed and analysed using an analysis of variance (ANOVA) model.⁶ The model will include dose as a factor.

For each PK parameter separately, the geometric least squares mean (GLSM) for each dose, p-values for the overall, and pairwise dose comparisons will be calculated. Residual plots will be produced to assess the adequacy of the model(s) fitted.

Examples of the SAS code that will be used are as follows:

Power Model Analysis

```
proc mixed data = <data in> alpha = 0.05;
  by parcatln parcat1 pkday paramn param;
  model lpk = ldose / cl residual ddfm = kr2;
  ods output solutionf = <data out>;
run;
```

Power Model Analysis (Between-subject Variability)

```
proc mixed data = <data in> covtest alpha = 0.05;
  by parcatln parcat1 pkday paramn param;
  class ldose;
  model lpk = ldose / cl residual ddfm = kr2;
  ods output covparms = <data out>;
run;
(Note: Pooled Geometric CV (%) = 100*(sqrt(exp(estimate)-1)))
```

Power Model Analysis (Lack of Fit Test)

```
proc mixed data = <data in>;
  by parcatln parcat1 pkday paramn param;
  class dose;
  model lpk = ldose dose / htype = 1 ddfm = kr2;
```

```
ods output tests1 = <data out>;
run;
```

ANOVA Model Analysis

```
proc mixed data = <data in> alpha = 0.05;
  by parcatln parcat1 pkday paramn param;
  class dose;
  model ldnpk = dose / cl residual ddfm = kr2;
  lsmeans dose / cl pdiff;
  ods output lsmeans = <data out>;
  ods output diffs = <data out>;
  ods output tests3 = <data out>;
run;
```

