The dietary state for dosing of KRP-A218 alone on Day 1 and KRP-A218 co-administered with itraconazole on Day 11 will be determined by comparing the PK data between fed and fasted state in Group A2a.

Itraconazole on Days 4 to 10, 12 and 13 will be administered in the fasted state. On Day 11, if it is determined that KRP-A218 will be dosed in the fasted state, then KRP-A218 will be administered first and itraconazole will be administered second. If it is determined that KRP-A218 will be dosed in the fed state, then itraconazole will be dosed first; subjects will then receive breakfast at approximately 1 hour post itraconazole dose, and KRP-A218 will be dosed second following breakfast. The dose level of KRP-A218 will be confirmed based on the available safety, tolerability, and PK data in preceding Parts A and/or B of the study.

Number of Subjects:

Part A: 40 male subjects and 8 female subjects will be studied in 5 groups.

Part B: 40 male subjects will be studied in 4 groups.

Part C: 12 male subjects will be studied in 1 group.

Diagnosis and Main Criteria for Inclusion:

Healthy male and female subjects aged between 20 and 55 years (inclusive).

Investigational Products, Dose, And Mode of Administration Route:

Test Products: KRP-A218 1 mg tablet, and 10 mg tablet

Proposed Dose Levels:

Part A: Males: 1, 3 (fasted/fed), 6, 12, and a maximum dose of 24 mg of KRP-A218

Females: 3 mg of KRP-A218

Part B: Males: X, X, X, and X mg of KRP-A218 (over a period of 14 days)

Part C: Males: X mg of KRP-A218 (once on Days 1 and 11)

Administration Route: Oral**Reference Product and Mode of Administration Route (Parts A and B):**

Reference Product: placebo tablet

Administration Route: Oral**Concomitant Drug, Dose Level, and Administration route (Part C):**

Concomitant Drug: itraconazole 10 mg/mL oral solution

Proposed Dose Level: 200 to 400 mg of itraconazole (200 mg twice on Day 4 and 200 mg once daily on Days 5 to 13)

Administration Route: Oral**Duration of Subject Participation in the Study:**

Planned Screening Duration: up to 27 days.

Planned Study Duration (Screening to Follow-up):

Part A: up to 39 days, or up to 50 days for food-effect evaluation.

Part B: up to 52 days.

Part C: up to 49 days.

Endpoints:**Safety:**

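### The dose-proportionality rule ignores the width of the slope interval and allows unplanned narrowing of the dose range, so moderate departures become easier to pass as doses are dropped

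*SAP*

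**What the plan says.** SAP 8.5.3.1 regresses the log of each PK parameter on log dose, in Part A (Day 1) and Part B (Day 14), and reports the slope with a 95% CI. The decision has two conditions: "If the assumption of linearity is ruled acceptable and the 95% CI for the slope spans 1". When both are met, "it will be deemed that there is no statistical basis to conclude a lack of proportionality". No margin or precision requirement is attached.

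Linearity is judged from diagnostic plots together with a lack-of-fit test ("the lack of fit 2-sided p-value >0.05"). The pharmacokineticist may also judge it by eye. Of that review the SAP says "This assessment may override the statistical assessment", with any such case described in the CSR. If linearity is rejected, the dose-normalised parameters go to an ANOVA.

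The full dose range is the planned analysis. Narrowing is allowed where data are insufficient at some levels, and also where "the dose proportionality is not concluded for the full dose range, analysis across narrower dose range may be explored". The SAP does not say which doses are dropped first, how many levels must remain, or how the narrower result is labelled.

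**The concern.** A rule of this kind rewards imprecision: the wider the interval, the more easily it includes 1. Removing dose levels takes away both subjects and spread in log dose, so each narrower range is a weaker test than the one before it. The narrowing clause is also triggered by the unfavourable result it can replace. A full-range finding of non-proportionality could therefore be followed by a sub-range that earns the favourable wording mainly because it holds less information.

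Linearity is used in this programme. Protocol 3.5 (Tables 4 and 6) scales exposure from the 6 mg group on that assumption, and Protocol 3.4 gives linear PK as a reason for single doses in Part C. SAP 8.5.3.1 is where the assumption is formally examined.

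**Working it through.** The documents state no power, error rate or precision target for this analysis, so there is no figure to reproduce.

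**Inputs**
- Doses: "Part A: Males: 1, 3 (fasted/fed), 6, 12, and a maximum dose of 24 mg of KRP-A218" (Protocol synopsis).
- 6 active subjects per level (Protocol 3.1.1). The female group A2b is left out.
- Between-subject CV of AUC0-∞: 18.6% at 1 mg, 30.1% at 3 mg fasted, 28.4% at 6 mg (Protocol Table 3). Values of 19%, 28% and 30% are used.
- Assumed: one constant true slope, a common CV, all active subjects evaluable.

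**Precision of the slope**

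SD = sqrt(ln(1 + CV²)), which is 0.275 at CV 28%. SE = SD / sqrt(Sxx), with Sxx the sum of squares of log dose over subjects. Half-width = t(0.975, N − 2) × SE.
- 1-24 mg: Sxx = 6 × 6.060 = 36.36; SE = 0.0456; half-width = 2.048 × 0.0456 = 0.093.
- 6-24 mg: Sxx = 6 × 2 × 0.693² = 5.77; SE = 0.1144; half-width = 2.120 × 0.1144 = 0.243.
- 1-6 mg: half-width 0.186.

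For example, an estimated slope of 1.20 over 6-24 mg has a CI of 0.957 to 1.443. It includes 1 and meets the slope condition. As a ratio of dose-normalised exposure between the ends of the range, r^(slope − 1) with r = 4, the CI runs from 4^(−0.043) = 0.94 to 4^0.443 = 1.85.

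**Chance of passing**

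The full-range column is the noncentral-t probability that the CI covers 1. The other columns are simulated and require both that the CI covers 1 and that the lack-of-fit p-value exceeds 0.05. Five levels give six runs of three or more consecutive doses, counting the full range. Dropping top doses only leaves 1-24, 1-12 and 1-6 mg.

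| True slope | 24^(slope − 1) | Full range, CV 19% / 28% | Some run of ≥3 levels, CV 19% / 28% | Top doses dropped only, CV 28% |
|---|---|---|---|---|
| 1.1 | 1.37 | 13% / 44% | 97% / 99% | 84% |
| 1.2 | 1.89 | 0% / 1% | 59% / 91% | 42% |
| 1.3 | 2.59 | 0% / 0% | 10% / 55% | 10% |
| 1.5 | 4.90 | 0% / 0% | 0% / 3% | 0% |

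At CV 30% the fourth column reads 93%, 64% and 6% for slopes 1.2, 1.3 and 1.5. Slopes of 0.9, 0.8 and 0.7 mirror 1.1, 1.2 and 1.3. Leaving out the lack-of-fit condition changes little (93% instead of 91% at slope 1.2, CV 28%). If the top dose were the 17 mg estimated in Protocol 3.5, the full-range CI would cover 1 in 3% at slope 1.2 and CV 28%.

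**The case against.** The strongest reply is that the SAP is more careful than the criticism implies. The wording is that of non-rejection and does not claim that proportionality is shown. Linearity must be accepted first. The full range is the planned analysis, and narrowing is optional. The slope, its 95% CI, log-log plots with the unit-slope line and dose-normalised plots are all specified, and SAP 8.1 urges caution because the study is not powered. All of this is correct. It means that a wide interval would be visible to an attentive reader. It does not change a conclusion sentence that is the same for a tight and a wide interval, and it supplies no rule or label for the narrower ranges.

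Second, the constant-slope assumption makes every sub-range pass an error. The data so far look proportional: AUC0-∞ per mg in Protocol Table 3 is 210, 564/3 = 188 and 1230/6 = 205 at 1, 3 and 6 mg. A departure confined to the top doses is plausible, and narrowing can then be informative. If exposure were proportional to 12 mg and 1.6-fold high at 24 mg, 1-12 mg would pass in about 91%, correctly, and 6-24 mg in about 17%. This stands. It is a reason to keep narrower ranges as labelled exploration, and it means that the table describes how the rule behaves and does not predict this drug's result.

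Third, a reader might infer that later doses hang on this verdict. The documents do not support that. Doses in this trial follow observed and predicted exposures with fixed caps (Protocol 3.5 and 3.7), and PK in Parts A and B is a secondary objective.

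**Conclusion.** The point holds for moderate departures, with slopes of about 1.1 to 1.3 or the mirror values below 1. At slope 1.2, trying every run of three or more doses raises the chance of a favourable result from about 1% to 91% at CV 28%, and from 0% to 59% at CV 19%. These are chances that some range would pass if all were tried; a more disciplined order gives less (42% when only top doses are dropped at CV 28%).

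A reader might go further and infer that some range will pass almost whatever the true departure. The figures do not support that: with three or more levels, slope 1.5 passes in 3% at CV 28% and in 6% at CV 30%. The SAP sets no floor on the number of levels, and pairs of doses would pass far more often (93% at slope 1.5, CV 28%). However, nothing in the SAP says that pairs would be used, and even then slope 2.0 passes in only 7%. Nor does the SAP declare proportionality whenever the CI covers 1, given the linearity condition and the hedged wording.

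The results rest on a constant slope, CVs of 19-30%, 6 evaluable active subjects per dose and a 24 mg top dose. Part B doses are not set, so its figures cannot be fixed, but the same rule applies there.

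**What to change.** In SAP 8.5.3.1:
1. Make the full-range slope and 95% CI the reported conclusion for each parameter, whatever narrower analyses follow.
2. For each range tested, report r^(slope − 1) with its CI, where r is the ratio of highest to lowest dose. Describe the result by that estimate and interval instead of by whether the slope CI includes 1.
3. Show any narrower range beside the full-range result, labelled post hoc.
4. Where the visual review overrides the lack-of-fit test, present both the power-model and the ANOVA results.

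No equivalence limit is needed, and a tight one would not suit this sample size. As an illustration with an assumed limit of 1.25 on the exposure ratio, the slope would have to lie within 1 ± ln(1.25)/ln(24) = 1 ± 0.070. The 90% half-width over 1-24 mg at CV 28% is 0.078, so a truly proportional drug would pass in only about 3%.

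The cost is SAP wording, one derived column and, after an override, one extra table. The downside is that a wide interval will read as inconclusive.

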8.5.3.2. Food Effect Assessment (Part A)

A statistical analysis will be conducted to investigate the food effect on the treatment by comparing '3 mg KRP-A218 (Fed Male)' (test treatment) to '3 mg KRP-A218 (Fasted Male)' (reference treatment).

The ln-transformed⁵ AUC_{0-tlast}, AUC_{0-∞}, and C_{max} on profile day 1 in Part A (only for plasma CCI) will be analysed using a mixed model.⁷ The model will include actual treatment as fixed effect and subject as a random effect.

For each PK parameter separately, the least squares mean (LSM) for each treatment, difference in LSMSs between the fed and fasted treatments, and corresponding 90% and 95% CIs will be calculated; these values will then be back-transformed to give the GLSM, ratio of GLSMs, and corresponding 90% and 95% CIs.

Additionally, the pooled estimate (across treatments) of the within-subject CV will be calculated, and residual plots will be produced to assess the adequacy of the model(s) fitted.

Examples of the SAS code that will be used are as follows:

Mixed Model Analysis

```
proc mixed data = <data in>;
  by parcatln parcat1 pkday paramn param;
  class trtan usubjid;
  model lpk = trtan / cl residual ddfm = kr2;
  lsmeans trtan / cl pdiff = control('1') alpha = 0.1;
  lsmeans trtan / cl pdiff = control('1') alpha = 0.05;
  random intercept / subject = usubjid;
  ods output lsmeans = <data out>;
  ods output diffs = <data out>;
  ods output covparms = <data out>;
run;
```

8.5.3.3. Sex Effect Assessment (Part A)

A statistical analysis will be conducted to investigate the sex effect on the treatment by comparing '3 mg KRP-A218 (Fasted Female)' (test treatment) to '3 mg KRP-A218 (Fasted Male)' (reference treatment).

The ln-transformed⁵ AUC_{0-tlast}, AUC_{0-∞}, and C_{max} on profile day 1 in Part A (only for plasma CCI) will be analysed using an ANOVA model.⁶ The model will include actual treatment as a factor.

For each PK parameter separately, the LSM for each treatment, difference in LSMs between the test and reference treatments, and corresponding 90% and 95% CIs will be calculated; these values will then be back-transformed to give the GLSM, ratio of GLSMs, and corresponding 90% and 95% CIs.

Additionally, the pooled estimate (across treatments) of the between-subject CV will be calculated, and residual plots will be produced to assess the adequacy of the model(s) fitted.

Examples of the SAS code that will be used are as follows:

ANOVA Model Analysis

```
proc mixed data = <data in>;
  by parcat1n parcat1 pkday paramn param;
  class trtan;
  model lpk = trtan / cl residual ddfm = kr2;
  lsmeans trtan / cl pdiff = control('1') alpha = 0.1;
  lsmeans trtan / cl pdiff = control('1') alpha = 0.05;
  ods output lsmeans = <data out>;
  ods output diffs = <data out>;
  ods output covparms = <data out>;
run;
```

8.5.3.4. Drug-drug Interaction Assessment (Part C)

A statistical analysis will be conducted to investigate the drug-drug interaction on the PK of KRP-A218 by comparing 'XX mg KRP-A218 + 200 mg Itraconazole' (test treatment) to 'XX mg KRP-A218' (reference treatment).

The ln-transformed⁵ AUC_{0-tlast}, AUC_{0-∞}, and C_{max} in Part C (only for plasma CCI) will be analysed using a mixed model.⁷ The model will include actual treatment as fixed effect and subject as a random effect.

For each PK parameter separately, the LSM for each treatment, difference in LSMs between the test and reference treatments, and corresponding 90% CI will be calculated; these values will then be back-transformed to give the GLSM, ratio of GLSMs, and corresponding 90% CI.

Additionally, the pooled estimate (across treatments) of the within-subject CV will be calculated, and residual plots will be produced to assess the adequacy of the model(s) fitted.

Examples of the SAS code that will be used are as follows:

Mixed Model Analysis

```
proc mixed data = <data in>;
  by parcat1n parcat1 paramn param;
  class trtan usubjid;
  model lpk = trtan / cl residual ddfm = kr2;
```

```
lsmeans trtan / cl pdiff = control('1') alpha = 0.1;
random intercept / subject = usubjid;
ods output lsmeans = <data out>;
ods output diffs = <data out>;
ods output covparms = <data out>;
run;
```

8.6. Pharmacodynamic Assessments

8.6.1. Pharmacodynamic Analysis

Data associated with serum phospholipid-C concentrations and faecal calprotectin will be reported in the TFLs.

Data associated with the exploratory metabolite profiling, biomarker analysis, pharmacogenetic analysis, and concentration QTc analysis will be reported separately.

8.6.2. Presentation of Pharmacodynamic Data

All serum phospholipid-C data and their changes from baseline will be listed.

Summary tables and boxplots by treatment and timepoint will be provided for all serum phospholipid-C data and their changes from baseline.

All faecal calprotectin data will be listed only.

Values recorded as <x, ≤x, >x, or ≥x will be displayed in the listings as recorded. For the derivation of listing flags, all calculations, and presentation in the figures, <x and ≤x values will be set to half of x whereas >x and ≥x values will be set to x.

8.6.3. Pharmacodynamic Statistical Methodology

No inferential statistical analyses are planned.

8.7. Safety and Tolerability Assessments

8.7.1. Adverse Events

All AEs will be coded using the Medical Dictionary for Regulatory Activities (MedDRA) Version 24.0 (or higher if a new version is issued during the study; see the DMP for more details).

A treatment-emergent adverse event (TEAE) will be defined as an AE that starts during or after the first dose, or starts prior to the first dose and increases in severity after the first dose.

A treatment-related TEAE will be defined as a TEAE with a relationship of possibly related or related to the study treatment, as determined by the investigator.

For Group A2a in Part A, the assignment of TEAEs to treatments will be as follows:

- A TEAE that starts or increases in severity during or after Period 1, Day 1 dosing and prior to Period 2, Day 1 dosing will be assigned to '3 mg KRP-A218 (Fasted Male)'.
- A TEAE that starts or increases in severity during or after Period 2, Day 1 dosing will be assigned to '3 mg KRP-A218 (Fed Male)'.

For Part C, the assignment of TEAEs to treatments will be as follows:

- A TEAE that starts or increases in severity during or after Day 1 dosing and prior to Day 4 dosing will be assigned to 'XX mg KRP-A218 Alone'.
- A TEAE that starts or increases in severity during or after Day 4 dosing and prior to Day 11 dosing will be assigned to '200 mg Itraconazole Alone'.
- A TEAE that starts or increases in severity during or after Day 11 dosing will be assigned to 'XX mg KRP A218 + 200 mg Itraconazole'.

All AEs will be listed. In addition to the data recorded in the database, the listings will include derived onset time and duration. Onset time will be calculated from the time of the last associated dose for TEAEs only. Where the last associated dose is referring to the last dose received prior to the start of a TEAE.

The frequency of subjects with TEAEs and the number of TEAEs will be summarised for the following categories:

- TEAEs (overall, serious, leading to discontinuation, and leading to death) by treatment
- TEAEs by severity and treatment
- Treatment-related TEAEs (overall, serious, leading to discontinuation, and leading to death) by treatment
- Treatment-related TEAEs by severity and treatment

The frequency of subjects will be summarised separately for TEAEs and treatment-related TEAEs by the following:

- System organ class, preferred term, and treatment
- Preferred term and treatment

For the AE data the following rules will apply:

- For the derivation of treatment-emergent status (applicable to all AEs): If the start date/time of an AE is incomplete or missing, an AE will be assumed to not be a TEAE, unless the incomplete start date/time or the end date/time indicates an AE started after the first dose.

- For the derivation of treatment-related status (applicable to TEAEs only): If the study treatment relationship for a TEAE is missing, a TEAE will be assumed to not be a treatment-related TEAE.
- For the derivation of onset time (applicable to TEAEs only): If the start date/time of a TEAE is missing, onset time will not be calculated. If the start date/time of a TEAE is incomplete, where possible, the minimum possible onset time will be calculated and presented in ' \geq DD:HH:MM' format (eg, if the date/time of the last associated dose is 01MAY2019/08:00 and recorded start date/time of a TEAE is 03MAY2019, then the minimum possible onset time will be calculated by assuming a TEAE started at the first hour and minute of 03MAY2019 [03MAY2019/00:00], thus will be presented as onset time \geq 01:16:00 in the listing). If the start date of a TEAE is the same as the date of the last associated dose but the start time of a TEAE is missing, an onset time will be presented as ' \geq 00:00:01'. Any clock changes will be accounted for in the derivation.
- For the derivation of duration (applicable to all AEs): If the end date/time of an AE is missing, duration will not be calculated. If the start or end date/time of an AE is incomplete, where possible, the maximum possible duration will be calculated and presented in ' \leq DD:HH:MM' format (eg, if the start of an AE date/time is 01MAY2019/08:00 and its recorded end date/time is 03MAY2019, then the maximum possible duration will be calculated by assuming an AE ended at the last hour and minute of 03MAY2019 [03MAY2019/23:59], thus will be presented as duration \leq 02:15:59 in the listing). Any clock changes will be accounted for in the derivation.
- For the calculation of TEAE summary statistics: If the severity of a TEAE is missing, that TEAE will be counted under the 'missing' category.
- For the calculation of TEAE summary statistics: If a subject experienced multiple TEAEs with the same preferred term for the same treatment, this will be counted as 1 TEAE for that treatment under the maximum severity recorded.

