Overall, 48 subjects will be studied in 5 groups (Groups A1 to A5); Groups A1, and A3 to A5 will consist of 8 male subjects, and Group A2 will consist of 16 subjects split into 2 subgroups (Group A2a [male subjects only] and Group A2b [female subjects only]) that will consist of 8 subjects each.

Potential subjects will be screened to assess their eligibility to enter the study within 28 days prior to the first dose administration. Each subject will participate in 1 treatment period only, except for Group A2a, where each subject will participate in 2 treatment periods where doses of KRP-A218 will be separated by an interval of 7 to 10 days (up to and including Day -1 of Treatment Period 2). The washout period may be extended depending on the observed apparent terminal elimination half-life ($t_{1/2}$) of CCI [REDACTED]. Subjects will reside at the study site from Day -1 (the day before dosing) to Day 4 of each treatment period.

All subjects will return for a follow-up visit 7 to 10 days after their final dose. The follow-up period may be extended depending on the observed $t_{1/2}$ of CCI [REDACTED]. In each of Groups A1, A2a, A2b, and A3 to A5, 6 subjects will receive KRP-A218 and 2 subjects will receive placebo. In Groups A1, A2b, and A3 to A5, all doses will be administered in the fasted state on the morning of Day 1. For Group A2a, Period 1, Day 1 doses will be administered in the fasted state and Period 2, Day 1 doses will be given 30 minutes after starting a standard high-fat breakfast. Each subject in Groups A1, A2b, and A3 to A5 will receive only a single dose of KRP-A218 or placebo during the study. In Group A2a, subjects will have the same treatment in both periods, such that each subject will receive 2 single doses of KRP-A218 or placebo during the study.

All groups in Part A (with the exception of Group A2a in Treatment Period 2) will receive the investigational medicinal product (IMP) using a sentinel approach. For each group, 2 subjects (1 KRP-A218 and 1 placebo) will receive the IMP at least 24 hours before the remaining subjects.

Part B:

There will be 4 groups, consisting of male subjects. Part B may overlap with Part A.

Overall, 40 subjects will be studied in 4 groups (Groups B1 to B4), with each group consisting of 10 male subjects. Part B may start after completion of Group A3, at dose equal to or less than given in Groups A1 to A3.

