3.3. Additional Groups

Following review of the safety, tolerability, and PK data, additional dose groups (where systemic exposure is not expected to exceed that stated in the dose escalation stopping criteria as detailed in [Section 3.7](#)) may be added to the study. Up to 3 further groups of 8 subjects (6 KRP-A218 and 2 placebo) in Part A and 3 further groups of 10 subjects (8 KRP-A218 and 2 placebo) in Part B may be added. The requirement for additional groups will be agreed with the Sponsor and documented in the trial master file (TMF).

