In each of Groups A1 to A5, 6 subjects will receive KRP-A218 and 2 subjects will receive placebo in accordance with a randomisation schedule. In Groups A1, A2b, and A3 to A5, all doses will be administered in the fasted state on the morning of Day 1. For Group A2a, Period 1, Day 1 doses will be administered in the fasted state and Period 2, Day 1 doses will be given 30 minutes after starting a standard high-fat breakfast. Each subject in Groups A1, A2b, and A3 to A5 will receive only a single dose of KRP-A218 or placebo during the study. In Group A2a, subjects will have the same treatment in both periods, such that each subject will receive 2 single doses of KRP-A218 or placebo during the study.

All groups in Part A (with the exception of Group A2a in Treatment Period 2) will receive the study treatment using a sentinel approach.

The total duration of study participation for each subject (from screening through follow-up visit) is anticipated to be up to 39 days (Groups A1, Group A2b [female subjects only], A3 to A5) or up to 50 days (Group A2a; male subjects only).

[figure not shown]
An overview of the study design is shown in [Figure 1](#) and [Figure 2](#), and the planned dose levels in [Figure 5](#).

Figure 1: Study Schematic (Part A; Groups A1, A2b [Female subjects Only], and A3 to A5)

*CRU = Clinical Research Unit

The follow-up period may be extended depending on the observed $t_{1/2}$ of CCI [REDACTED]

Figure 2: Study Schematic (Part A; Group A2a [Male subjects Only])

The washout and follow-up periods may be extended depending on the observed $t_{1/2}$ of CCI

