6. STUDY TREATMENTS

6.1. Part A

The study treatment names and ordering to be used in the TFLs for Part A are presented in [Table 1](#). The study treatment sequence names and ordering to be used in the TFLs for Part A are presented in [Table 2](#).

Table 1: Presentation of Study Treatments in TFLs (Part A)

Group	Study Treatment	Order in TFLs
A1 to A8	Placebo ^a	1
A1	1 mg KRP-A218 (Fasted Male)	2
A2a	3 mg KRP-A218 (Fasted Male)	3
A2b	3 mg KRP-A218 (Fed Male)	4
A3	3 mg KRP-A218 (Fasted Female)	5
A4	6 mg KRP-A218 (Fasted Male)	6
A5	12 mg KRP-A218 (Fasted Male)	7
A6 ^b	24 mg KRP-A218 (Fasted Male)	8
A7 ^b	XX mg KRP-A218 (Fasted Male)	9
A8 ^b	XX mg KRP-A218 (Fasted Male)	10
	XX mg KRP-A218 (Fasted Male)	11

^a Placebo will be pooled across all groups, regardless of sex and the fasting condition

^b Optional group, to be included if required

Table 2: Presentation of Study Treatment Sequences in TFLs (Part A; Food-effect Group Only)

Group	Study Treatment Sequence	Order in TFLs
A2a	Placebo (Fasted Male) / Placebo (Fed Male)	1
A2a	3 mg KRP-A218 (Fasted Male) / 3 mg KRP-A218 (Fed Male)	2

All TFLs will be based on actual treatments (eg, if subject was assigned to receive placebo but was wrongfully dosed with active treatment they would be summarised and listed under active treatment).

All dose levels described above are the potential dose levels, and therefore are subject to change. The TFLs will reflect the dose levels utilised in the study, and these will be displayed in increasing order.

All fasting conditions described above are the potential fasting conditions, and therefore are subject to change. The TFLs will reflect the fasting conditions utilised in the study.

The food-effect group described above is the potential food-effect group, and therefore is subject to change. The TFLs will reflect the food-effect group utilised in the study.

The sex-effect group described above is the potential sex-effect group, and therefore is subject to change. The TFLs will reflect the sex-effect group utilised in the study.

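### SAP 8.7.1 sends Group A2a adverse events to 3 mg KRP-A218 columns without limiting the rule to subjects on active drug, in conflict with SAP 6.1 (minor)

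*SAP*

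**What the plan says.** SAP 8.7.1 introduces the rule with "For Group A2a in Part A, the assignment of TEAEs to treatments will be as follows". Two bullets follow. Events that start or worsen from Period 1 dosing until Period 2 dosing go to 3 mg KRP-A218 (Fasted Male). For later events, "A TEAE that starts or increases in severity during or after Period 2, Day 1 dosing will be assigned to" 3 mg KRP-A218 (Fed Male). There is no third bullet, and neither bullet mentions the treatment received.

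The Protocol synopsis gives the allocation: "In each of Groups A1, A2a, A2b, and A3 to A5, 6 subjects will receive KRP-A218 and 2 subjects will receive placebo". SAP 4.1 adds: "In Group A2a, subjects will have the same treatment in both periods". SAP Table 2 accordingly lists a placebo/placebo sequence for A2a beside the active one.

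SAP 6.1 sets the general rule: "All TFLs will be based on actual treatments". The footnote to SAP Table 1 says: "Placebo will be pooled across all groups, regardless of sex and the fasting condition".

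SAP 8.7.1 also sets defaults for incomplete data. An event whose start is missing or incomplete is taken as not treatment-emergent, unless the partial start or the end date/time indicates that it began after the first dose.

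**The concern.** The two bullets cover every time after first dosing, so read literally they send every A2a TEAE to a drug column, including those of subjects who never took the drug. SAP 6.1 sends the same events to pooled placebo. Both instructions cannot be followed for these subjects. SAP 8.7.1 is the specific rule for adverse events, and nothing in the SAP says which section prevails.

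Safety and tolerability is the primary objective of Parts A and B, adverse events head the endpoint list, and the by-treatment TEAE tables are where they are summarised. With six active subjects per column, one misplaced subject is visible. The data also exist: Protocol 1.3 reports that 8 males in A2a had been dosed fasted and fed by 27 August 2021. It gives no event counts by arm, so it does not show whether any A2a placebo subject had a TEAE.

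The onset default raises a smaller point. When onset cannot be placed relative to dosing, the event drops out of the TEAE tables, so the default can only lower the counts.

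**Working it through.** **Inputs**

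- Part A total: 48 subjects (SAP 4.1).
- Cohorts A1, A2a, A2b, A3, A4 and A5, each with 6 KRP-A218 and 2 placebo (Protocol synopsis).
- Optional groups: "Up to 3 further groups of 8 subjects (6 KRP-A218 and 2 placebo) in Part A" (Protocol 3.3).
- TEAE rates: none are given by arm. Any rate below is an assumption.

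**Reproducing the plan's total**

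6 cohorts × 8 = 48, which matches. Active: 6 × 6 = 36. Placebo: 6 × 2 = 12. With three optional groups, placebo is 12 + 3 × 2 = 18.

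**The two rules for an A2a placebo subject with a TEAE**

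| Time of event | SAP 8.7.1, literal | SAP 6.1 |
|---|---|---|
| Period 1 dosing until Period 2 dosing | 3 mg KRP-A218 (Fasted Male) | Placebo |
| From Period 2 dosing on | 3 mg KRP-A218 (Fed Male) | Placebo |

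**Size under the literal rule, with denominators by actual treatment**

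Each 3 mg male column has 6 subjects and pooled placebo has 12. Let k be the number of A2a placebo subjects with a TEAE in a given period, with all their events moved.

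- Added to that 3 mg male column: k/6. For k = 1, 16.7 points; for k = 2, 33.3 points.
- Removed from pooled placebo: k/12. For k = 1, 8.3 points; for k = 2, 16.7 points. With 18 placebo subjects and k = 1, the loss is 1/18 = 5.6 points.
- A subject with events in both periods would add 1/6 to both columns and still be lost only once from placebo.
- Ceiling: (6 + 2)/6 = 133%, an impossible percentage.

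**How likely it is to occur**

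The chance that at least one of the two placebo subjects has a TEAE in a period is 1 − (1 − p)². For assumed p of 10%, 25% and 50% it is 19%, 44% and 75%.

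**Illustration with equal true rates**

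The 3 mg male column is multiplied by 8/6 and pooled placebo by 10/12. At an assumed 25% in both arms, the 3 mg column shows 33.3% and placebo 20.8%: an apparent difference where there is none.

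**Onset default**

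Take a single-dose subject with an event dated Day 1, no start time, and an end on Day 2. The partial start does not show whether the event began before or after dosing. The end shows only that it was still present after dosing. The exception is not met, so the event is not a TEAE. SAP 8.7.1 does have an onset-time rule for a same-day start with missing time, but it applies only to events already classed as TEAEs and so does not recover this one. The documents give no rate of missing onset, so this cannot be sized.

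**The case against.** The strongest reply is that the SAP already resolves the point. SAP 6.1 applies to all tables without exception and pools placebo whatever the fasting state, so a placebo event needs no period rule. Only subjects on KRP-A218 have two labels, and the bullets exist to split those. A count of up to 8 over a denominator of 6 also shows that the literal reading was not intended, and could expose the error. The safety analysis is descriptive, all adverse events are listed, and dose escalation rests on the ongoing reviews in Protocol 3.6 and 3.7, not on these final tables. The TFL shells, which might settle the matter, are not among the documents.

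Most of this stands, and it limits the weight of the point. It does not remove the conflict: the specific rule omits a qualifier that it needs, and the reader has to supply it from another section.

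On onset, the reply is that such cases should be rare. Protocol 7.3.1 requires time of onset to be documented and has subjects asked at least daily while resident. That also stands.

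Three stronger readings are tempting, and the documents do not support them:

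- That the 3 mg male columns would become a mixture with one quarter placebo recipients, shifting in either direction. This requires the placebo subjects to move into the drug denominators. No section provides for that, and the actual-treatment rule in SAP 6.1 speaks against it.
- That counting missing causality as not related is an inconsistency, because missing severity has its own category. SAP 8.1.2 allows stated exceptions to the missing category, SAP 8.7.1 states one, and no planned summary is broken down by relationship category. A different choice would be a preference.
- That the onset default biases drug against placebo. It applies equally to both.

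**Conclusion.** The conflict between SAP 8.7.1 and SAP 6.1 is real, affects 2 of the 8 planned A2a subjects (2 of 12 planned Part A placebo subjects, 16.7%), and is minor. A reader might infer that the Part A tables will show placebo events under drug. The documents do not support that, because SAP 6.1 would probably lead a programmer to the right column.

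If the literal rule were followed, each A2a placebo subject with a TEAE would add 16.7 points to a 3 mg male column and take 8.3 points from pooled placebo. These figures rest on the planned allocation, on denominators by actual treatment, and on no optional groups being added. Under those denominators, misplacement can only raise the drug column and lower the placebo column.

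The onset default under-counts events of undetermined onset. It is worth reversing, but the effect is probably small and cannot be sized.

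**What to change.** 1. In SAP 8.7.1, limit the two A2a bullets to subjects who received KRP-A218, and add that TEAEs of A2a placebo subjects in either period go to the pooled Placebo column. Cost: one phrase and one sentence, with no analytical downside.

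2. In the same section, reverse the onset default: count an event with a missing or incomplete start as a TEAE unless the available dates/times show that it began before the first dose and did not worsen afterwards. Cost: one reworded sentence. Downside: events are recorded from consent, so a few pre-dose events may be counted. For active A2a subjects and for Part C, such an event may fit more than one treatment column, and the team should agree how to place it. A blanket rule of assigning it to the latest treatment is not recommended, because it would load the fed and itraconazole columns.

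Both changes should be made before unblinding, with a check that the TFL shells agree.
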